3. Able to speak, read and write fluently in English, assessed by the study coordinator at Carrier Clinic
4. Screened Negative for alcohol abuse and/or dependence
5. Able to provide informed consent, assessed by the study coordinator at Carrier Clinic
6. Referred for ECT
7. Not currently taking hypnotics or be prescribed hypnotics during the Nexalin trial.
8. Not pregnant or intending to become pregnant during the study
9. Committed to completion of the study.

TOTAL SUBJECTS ENROLLED

150

VULNERABLE POPULATIONS

No vulnerable populations (as defined by socio-economic status, geography, gender, age, disability status, and other populations identified to be at-risk for health disparities) will be recruited.

RECRUITMENT & RANDOMIZATION

As noted above, patients will be directly recruited from, and receive treatment at, the Carrier Clinic. Currently, the Carrier Clinic treats approximately 1,000 unique patients who receive ECT annually, resulting in 5,200 procedures performed per year. Randomization will occur in blocks, such that for every 20 subjects enrolled, 10 will receive Nexalin and 10 will receive Sham treatment.

COMPENSATION

No financial compensation will be provided to participants for participation in the trial.

PRIMARY OUTCOMES

Percent responders and non-responders to TES treatment or Sham TES treatment (who accepted or refused ECT) as assessed with the PHQ-9 (50% reduction or a score below 10).

SECONDARY OUTCOMES

Assess whether Nexalin TES produces significantly greater gains than Nexalin Sham for

1. Depression severity (as assessed with the PHQ-9, and the QIDS)
2. Anxiety severity (as assessed with the GAD-7 and the POMS)
3. Insomnia severity (as assessed with the ISI)

Finally, we will (post hoc) assess which baseline subject characteristics differentiate between responders and non-responders.

PROCEDURES

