	7	PHQ-9	1 min	●	●			
	8	GAD-7	1 min	●		●		
	9	POMS	10 min	●		●		
	10	FACES	1 min		●			
Clinician	1	Patient Enrollment	2-5 min	●				
	2	Procedure Tracking	2-5 min		●			
	3	Adverse Event	5 min				●	
	4	Clinician Information	2-5 min	●				
	5	SBJ d/c Form	2-5 min					●

ASSESSMENT OF SUBJECT CLINICAL STATUS

As noted above, patient status will be assessed at baseline, twice daily (pre-post each session), once daily, and once every three days. The instruments will be administered on-site via an internet data portal (constructed with RedCap).

Subject Measures. All self-report instruments used in the study are listed below along with their administration schedule and a brief explanation regarding what the instrument measures.

1. **Demographics** (*completed once at baseline / intake*): All subjects will report age, sex, education level, **race/ethnicity**, and other relevant demographic and socioeconomic information.

2. AFQ * CAGE (completed once at baseline / intake): These instruments are standard alcoholism screening tools. Subjects who screen positive for alcoholism will not be included in the study.
3. Patient Expectancy (completed at baseline): Subjects will be asked to rate on a 0-5 Likert scale the degree to which they agree with the following statements: (1) This treatment will work, (2) This treatment will help my depression, (3) This treatment will help my anxiety, (4) This treatment will help my sleep, (5) This treatment will improve my quality of life.
4. QIDS (completed at baseline and once every three days): The 16 item Quick Inventory of Depressive Symptomatology (QIDS) is designed to assess the severity of depressive symptoms. The QIDS is a self-administered instrument that assesses all the criterion symptom domains designated by the DSM-IV. The patient is asked to rate the severity and frequency of specific symptoms present over the last 7 days. Each item is interval scaled from 0 to 3. It takes approximately 5 to 7 minutes to complete and the total score is obtained by adding the scores. The summary score ranges from 0 to 27. Threshold values are as follows: \leq 9 (Not Depressed); 10-13 Mild Depression; Moderate to Severe Depression 14-17; $>$ 18 Severe Depression.

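### The QIDS scoring rule as written (add 16 items scored 0 to 3) gives 0 to 48, not the stated 0 to 27; the step that reduces 16 items to a 27-point total is missing

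*Combined protocol and SAP*

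**What the plan says.** All the scoring information is in one entry: Assessment of Subject Clinical Status, Subject Measures, item 4 (QIDS).

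- Length: "The 16 item Quick Inventory of Depressive Symptomatology (QIDS) is designed to assess the severity of depressive symptoms".
- Item scale: "Each item is interval scaled from 0 to 3".
- Rule for the total: "the total score is obtained by adding the scores".
- Range of the total: "The summary score ranges from 0 to 27".
- Severity thresholds: 9 or less is not depressed, then "10-13 Mild Depression; Moderate to Severe Depression 14-17", then above 18 for severe.

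The entry also says that the instrument "assesses all the criterion symptom domains designated by the DSM-IV". It does not say how many domains there are, or that domain scores rather than item scores are added.

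Under Secondary Outcomes the QIDS is one of two instruments for the first listed outcome: "Depression severity (as assessed with the PHQ-9, and the QIDS". It is collected at baseline and at three-day intervals. The Analysis Plan gives no scoring rule for any questionnaire.

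**The concern.** A reader who follows the entry literally sums 16 item scores, because item scores are the only scores it defines. That total cannot have the range the same entry gives. One of the statements must be wrong or incomplete, and whoever codes the variable has to guess which.

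At stake is the definition of a named secondary efficacy outcome. Change on a 48-point sum is not in the same units as change on a 27-point score. A reported mean difference, or any reading of a score against the printed thresholds, would mislead if the reader assumed the stated range. The two totals can also weight symptoms differently, so dividing by a constant would not in general convert one into the other.

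**Working it through.** **Inputs**, all from the QIDS entry: 16 items; item scores 0 to 3; total by addition; stated range 0 to 27; thresholds at 9, 10–13, 14–17 and above 18.

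**1. Try to reproduce the stated range.** Maximum = number of items × maximum per item = 16 × 3 = 48. Minimum = 16 × 0 = 0. The written rule gives 0 to 48, so the stated 0 to 27 is not reproduced. Ratio of maxima: 48 / 27 = 1.78.

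**2. Would a different item scale rescue it?** With 16 items summed:

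| Item scale | Total range |
|---|---|
| 0–1 | 0–16 |
| 0–2 | 0–32 |
| 0–3 (as stated) | 0–48 |
| 1–3 | 16–48 |

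None gives 0 to 27. Solving for the item maximum gives 27 / 16 = 1.69, which is not a whole number. No integer item scale starting at 0 works with 16 summed items.

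**3. What would give 27?** Keep the 0–3 scale and solve for the number of summed components: 27 / 3 = 9. The stated range therefore fits a plain sum of nine components scored 0 to 3. The document does not say what those components are, or how 16 items become nine.

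**4. Is the difference only a change of scale?** If every item feeds exactly one of nine components, the average is 16 / 9 = 1.78 items per component. That is not a whole number, so the components cannot all hold the same number of items. If instead only nine items count, seven (16 − 9) have no weight. In either case the raw sum weights items differently from the nine-component score.

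**5. What happens to the thresholds?** As a share of the maximum:

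| Score | Of 27 | Of 48 |
|---|---|---|
| 10 (lowest mild score) | 10 / 27 = 37% | 10 / 48 = 21% |
| 18 (edge of severe) | 18 / 27 = 67% | 18 / 48 = 38% |

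As an illustration only, take a patient who scores 1 on every item. The written rule gives 16 × 1 = 16, in the 14–17 band. Assume instead nine components, each equal to 1 (as they would be if each were a single item, a maximum or a mean). The total is then 9, in the not-depressed band. The reduction is my assumption, since the document gives none.

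**6. Coverage of the thresholds.** Checking every whole score from 0 to 27 against the bands as they appear, only 18 falls in no band.

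**The case against.** The strongest reply is that this list briefly describes named instruments and is not a scoring specification. The entry mentions symptom domains and prints the range, so its author probably had a component score in mind and left out a step. Anyone who summed all 16 items could notice a total above 27. Most of this stands. The likelier defect is an omitted step, not a wrong range. But the reduction is stated nowhere else in the document, and the range check catches only totals above 27; a raw sum of, say, 16 looks plausible.

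A reader might infer more than the text supports:

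- **That scores are being summed wrongly in REDCap.** The Assessments section says the site is built in REDCap and mentions summary data. The Confidentiality section describes the study websites as allowing data entry only. Nothing says where totals are calculated, or that they are coded from this entry. The error is conditional on the text being used as the rule.
- **That the treatment comparison is invalid.** One consistent sum applied in both arms keeps the randomised comparison internally valid. What changes is the scale, the weighting and comparability with 0-to-27 scores.
- **That patients would be misclassified in the trial.** No eligibility criterion, outcome or planned analysis uses a QIDS band, and the shift is not universal: a patient who scores 0 throughout scores 0 either way.
- **That the document overstates the maximum.** It states 27. The 48 is derived from its rule.
- **That the gap at 18 is a drafting error.** The text was extracted from PDF, and a greater-than-or-equal sign may have been lost.

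**Conclusion.** The contradiction is real and can be checked within a single entry. The written rule yields 0 to 48 and the stated range is 0 to 27. The latter fits a plain sum of nine 0-to-3 components, but the step that would produce them is absent. Nine components is an inference from 27 / 3, and the documents do not settle how they are formed.

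If the total were coded as written, the outcome's maximum would be 1.78 times the stated one, with different item weighting and thresholds that no longer carry their stated meaning. The consequence is confined to a secondary outcome. The primary outcome is response "as assessed with the PHQ-9 (50% reduction or a score below 10", and the Procedures section bases non-response by six treatments on the PHQ-9 too, so neither is affected.

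This should be corrected because it leaves a named efficacy outcome without a usable definition and is cheap to resolve. It does not threaten the trial's main conclusion.

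**What to change.** Replace the clause about adding the scores with a rule that states which item or component scores enter the QIDS total, and how the 16 items are reduced (for example, whether some are dropped or combined, and by what operation), so that the rule yields the stated 0 to 27. The sponsor must take this from the instrument's own scoring instructions, since the protocol does not contain it.

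Then confirm, wherever the total is calculated, that the code follows that rule and cannot return a value above 27. As a minor check, confirm in the source file whether the top band includes 18.

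The cost is one sentence in the protocol and one check of the derived variable. If item-level responses are kept, any totals already calculated can be rescored without collecting new data.

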TES (as administered by the Nexalin apparatus) may be a viable alternative to ECT. A prior randomized, controlled trial compared antidepressant medication with Sham TES, Placebo with Nexalin at a lower dose, and Placebo medication with Nexalin at a higher dose. All three conditions showed remission of depressed mood by the end of treatment and maintenance of remission status following 12 weeks of follow-up. Thus, the effect sizes for Nexalin treatment were comparable to antidepressant medication. It should also be noted that the Nexalin device has undergone extensive safety analysis indicating that the device is safe for its intended use. Additionally, the classification of the device places it into a nonsignificant risk (low risk device) category. A review of Phase III Pivotal Clinical Trials (with a follow up period of one year) demonstrates that Nexalin TES Therapy does not result in any significant adverse events or side effects. In fact, there was no significant difference between reported events in the placebo group and reported events in the active treatment group.

[figure not shown]
Since the direct electrical stimulation represents a similar mechanism of action to ECT, and Nexalin has not only demonstrated effectiveness in depression but also has a much better safety profile than ECT, it is possible that Nexalin treatment could be a viable, more acceptable, alternative to ECT.

STUDY GOAL

Determine whether Nexalin TES is a viable alternative to ECT in subjects who do and do not accept ECT treatment.

STUDY DESIGN

A 2x2 factor Randomized Controlled Trial with block randomization. Inpatient subjects at the Carrier Clinic who are referred for ECT will be recruited, typed regarding their acceptance of ECT, and randomized to either treatment with TES or to a Sham condition. Treatment non-responders in either condition will continue as inpatients at the Carrier Clinic until they reach acceptable levels of functioning to be discharged. For additional details, see "procedures" section of this document.

STUDY DURATION

The study will last up to 2 years. This will allow sufficient time for recruitment and completion of all subjects.

TARGET POPULATION

Patients diagnosed with major depressive disorder (MDD) who have failed antidepressant therapy with one or more medications and are referred for ECT.

INCLUSION CRITERIA

To be included in the study, patients must be:

1. In-patients at the Carrier Clinic
2. Adults over age 18 and under age 65

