Treatment. As noted above, Nexalin TES or Sham TES will be administered twice per day (9am noon and then again 2pm-5pm), Monday through Friday, over the course of 3-10 days. Each patient will receive a minimum of 6 treatments and may receive up to 20 treatments depending on whether an adequate treatment response is observed during the first 6 session (this is based on the assessments overseen by the Penn staff based on the AM/PM PHQ-9 evaluations). All procedures will be performed at the Carrier Clinic facility by licensed

personnel with experience providing care to medication non-responders and will be specially trained on using the Nexalin equipment. Nexalin TES involves placing three conductive pads on the head (one on the forehead and one behind each ear). The patient then sits as the device administers the current through the pads. The waveform generated by the Nexalin device is a high frequency square wave (100 kHz), which has its amplitude modulated at a frequency of 77.5 Hz. Amplitude of the waveform (square wave pulse) is controlled to range from 0 to 4 mA peak current (off is 0 mA and on is 4mA). Each treatment session will last for 40 minutes. The treatment is not expected to be painful, but some individuals may experience discomfort (i.e. tingling and burning). In most cases, patients cannot feel when the pads are activated. The Sham treatment will be identical with the exception that there will be no current through the electrodes. Since the Nexalin treatment is undetectable, this will exactly mimic active treatment.

Assessments. Assessments will be made at baseline (pre-treatment), twice daily, once daily, and once every 3 days (6 sessions). All assessments will be administered on-line via two web-sites dedicated to the study (1 website for the subjects and one website for the clinical staff). The subject web-site will contain 10 questionnaires. The staff website will contain 5 forms.. See figure below for a specification of the specific instruments and schedule of administration. The site itself will be built using Research Electronic Data Capture (REDCap) software. Note: All data acquired via this method (raw and summary data) will not be available to the Carrier Clinic collaborators during the study.

	#	Instrument	Time Required	Baseline	Each Session	Q 3 days	Pre-Post	PRN
Patient	1	Demographics	5 min	●				
	2	AFQ & CAGE	2 min	●				
	3	Patient Expectancy	1 min	●				
	4	QIDS	5 min	●		●		
	5	ISI	2 min	●			●	
	6	SAFETEE	5-10 min	●		●		

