5. ISI (Completed at baseline and at the end of treatment): The Insomnia Severity Index is a brief insomnia screening tool that is the gold standard for quantifying severity of clinical insomnia symptoms. This will be administered at the beginning and end of treatment (e.g., 1st and 10th session).
6. SAFTEE (completed once every 3 days): The Systematic Assessment of Treatment-Emergent Effects was developed by the NIH to comprehensively catalog any physical symptoms experienced during psychiatric clinical trials along 16 subscales. This measure will be used to systematically measure symptoms and symptom categories.
7. PHQ-9 (completed in the AM and PM session): The Patient Health Questionnaire 9 is a brief, well-validated screening tool for depression. It has shown good reliability and validity for likely depression diagnosis and provides a means of assessing depression severity. The instrument in the present study has been modified so that it may be 1) administered twice daily and 2) used to track nightly sleep via 4 sleep related items
8. GAD7 (completed at baseline and once every 3 days): The Generalized Anxiety Disorder 7 questionnaire is a brief global screening measure of anxiety. It is well validated and is a standard screening tool for anxiety. This scale will allow for separate characterization of anxiety symptoms in addition to depression.
9. POMS (completed at baseline and once every 3 days): This is a 37-item adjective checklist where each item is rated on a 0-4 unipolar scale that ranges from not-at-all to extremely. The scored instrument provides values for six constructs including: tension-anxiety; depression-dejection; anger-hostility; fatigue-inertia; vigor-activity; and confusion-bewilderment. The outcome variables are measured in terms of the 6 factors and a total score, which are arrayed as T-Scores (standardized means of 50 +/-10).
10. “Faces” Mood Rating Scale (completed daily pre-post to each TES session): This is a single item 7 point bipolar rating scale for mood (from very happy to very sad). The measure is arrayed from -3 to +3.

Clinician Measures. All the clinician instruments to be used in the study are listed below along with their administration schedule and brief explanation regarding what the instrument measures

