Nexalin and Sham: To avoid headaches and nausea, only lower currents will be used (4mA) in association with active treatment. Patients shall also be instructed to alert the technician if they experience headache or nausea. If the condition continues, treatment will be discontinued. Burn occurrence is avoided by using lower current, square wave pulses large area electrodes, and by the device's ability to monitor electrode impedance and stop treatment if electrode contact is poor. The device generates no DC current and thus no significant electrolysis will occur in the electrodes. The AC waveform is passed through a charge blocking capacitor to patient electrodes for further patient protection. Rarely, patients have been noted to experience excitability or heightened nervousness during treatment. The technician administering treatment shall be trained to identify such cases and instructed to decrease current or discontinue treatment as appropriate. If agitation persists for a patient, the licensed health care practitioner may discontinue treatment. Rashes from specific electrodes may occur in patients sensitive to the adhesives used. The possibility of such rashes or skin irritation has been minimized by maintaining charge balance in the output waveform so significant electrolysis does not occur at the electrode/skin interface, and by using glycerol coated electrodes that result in little or no skin irritation. Additionally, collection of patient sensitivity information prior to treatment may avoid adverse reactions in patients with a prior history. Before treatment, patients shall be instructed to alert the

technician if they experience any pain or discomfort. The technician shall also examine the area of electrode contact before and after treatment and note any adverse reactions. Patients will be instructed not to remove electrodes during treatment. Electrodes and wires to the device shall be placed such that accidental removal of electrodes during treatment is unlikely. Finally, patients will be shown the "current off" button on the device and instructed to use this button if they feel it is necessary to terminate treatment prematurely.

Questionnaires, interviews, and body measurements will be conducted by licensed professionals who are experienced working with mentally ill patients. It is hoped that the courtesy, professionalism, and experience of these staff members allays any concerns regarding issues arising from the assessments.

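### No SAFTEE is scheduled at discontinuation or end of treatment, so a patient who stops for side effects before about session 6 has no post-baseline SAFTEE

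*Combined protocol and SAP*

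**What the plan says.** **SAFTEE schedule.** Under Assessment of Subject Clinical Status, Subject Measures item 6 reads "SAFTEE (completed once every 3 days". Its stated role is: "This measure will be used to systematically measure symptoms and symptom categories". The schedule table under Procedures (Assessments) marks it at baseline and every 3 days, and nowhere else. The same section equates the interval with sessions: "once every 3 days (6 sessions". By contrast, the ISI (item 5) has an end-of-treatment administration.

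**Treatment course.** Under Procedures (Treatment), "Nexalin TES or Sham TES will be administered twice per day" over 3-10 days, and "Each patient will receive a minimum of 6 treatments and may receive up to 20 treatments".

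**Stopping for side effects.** Protection Against Risks says of headache and nausea: "If the condition continues, treatment will be discontinued". For agitation the wording is permissive: the technician may lower the current or stop, and the practitioner may discontinue if it persists. No minimum number of sessions is attached to either.

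**Other records.** Clinician Measures lists an Adverse Event form and an SBJ d/c form, both completed as needed, and a Procedure Tracking form with comments at every session. Protection Against Risks adds a check of the electrode site before and after treatment.

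**Analysis.** Secondary Outcomes covers depression, anxiety and insomnia. The Analysis Plan covers response rates and the comparison of responders with non-responders. Neither names a safety or tolerability analysis.

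**The concern.** SAFTEE is the only instrument that asks patients in both arms the same full list of symptoms, whether or not they volunteer a complaint. Several of the effects named under Potential Study Risks (headache, nausea, agitation) depend largely on the patient reporting them, so solicited collection matters.

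Under the present schedule, the patients most likely to lack a post-baseline SAFTEE are those who leave early because of a side effect. The missingness would then be caused by the harm being measured. Sham delivers no current, so stops caused by current can arise only in the TES arm, and a comparison of available SAFTEE data would tend towards no difference.

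This matters because the Background rests part of the rationale on tolerability: "Nexalin has not only demonstrated effectiveness in depression but also has a much better safety profile than ECT". The randomised sham comparison is where this trial could examine the tolerability of TES. An inventory not collected at exit cannot be recovered at analysis.

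**Working it through.** **1. Reproduce the plan's interval.** 2 sessions per day × 3 days = 6 sessions, which matches "once every 3 days (6 sessions". The course is 3 × 2 = 6 to 10 × 2 = 20 sessions, which matches the stated minimum and maximum.

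**2. Place the SAFTEE points.** Multiples of 6 up to 20 are sessions 6, 12 and 18. The plan does not say whether the form is given before or after the session, hence about.

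**3. Who is missed.**
- Stop at sessions 1-5: no scheduled post-baseline SAFTEE.
- Stop between later points: nothing covers the sessions since the last one.
- Full course: 20 − 18 = 2 sessions (one treatment day) uncovered, which is minor.
- Non-responders taken off at session 6: the exit coincides with a scheduled SAFTEE, so no gap.

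**4. Size, by illustration.** The documents give no early-stop rate and no side-effect rate, so both are assumed. Let *d* be the share of an arm that stops for side effects before the first post-baseline SAFTEE, and *q* the symptom rate among those assessed. Early stoppers are all taken as symptomatic.

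- Rate seen in available SAFTEE data: *q*
- True rate: *d* + (1 − *d*)*q*
- Understatement: *d*(1 − *q*)

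Blocks of 20 split 10:10, so 150 enrolled gives about 75 per arm. With *q* = 15%:

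| *d* | Patients without post-baseline SAFTEE (75 × *d*) | True rate | Understatement |
|---|---|---|---|
| 2% | 1.5 | 0.02 + 0.98 × 0.15 = 16.7% | 1.7 points |
| 5% | 3.75 | 0.05 + 0.95 × 0.15 = 19.25% | 4.25 points |
| 10% | 7.5 | 0.10 + 0.90 × 0.15 = 23.5% | 8.5 points |

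With *q* varied from 10% to 30%, the understatement is 1.4-1.8 points at *d* = 2%, 3.5-4.5 at 5% and 7.0-9.0 at 10%.

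**5. Between arms.** The difference TES minus sham is understated by *d*(1 − *q*) in TES less the same quantity in sham. If no sham patient stops early, the whole of the table applies. With *d* = 5% in TES, 2% in sham and *q* = 15% in both, it is 4.25 − 1.7 = 2.55 points. With equal *d* and *q* in both arms it is zero.

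**The case against.** A reader might infer that early stoppers leave no post-baseline record and that the trial's tolerability result is therefore overstated. The documents support neither step. A side effect that ends treatment should appear on the Adverse Event form (description, onset, severity, symptoms, outcome), the SBJ d/c form and the per-session tracking form, and a skin reaction at the electrode-site check. What is missing is the solicited inventory. Overstatement would need a by-arm summary built on available SAFTEE data without the Adverse Event forms, and the plan specifies no such analysis. The lack of a specified analysis does not protect against the problem, though: nothing rules out that summary or says how the two sources combine.

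Early exit is itself partly an inference. "Each patient will receive a minimum of 6 treatments and may receive up to 20 treatments", read literally, takes everyone to the session-6 SAFTEE. Protection Against Risks says treatment stops, not that assessment stops, and elsewhere uses the word treatment for a single session. This stands as a contradiction to be resolved. Even so, no sentence provides for a SAFTEE after a patient has stopped.

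The rates used above are assumptions, and the document's own statements point to lower ones. Potential Study Risks ties headache and nausea to higher currents than those used here, and the Background reports no significant difference in events from placebo. That stands, and at a 2% early-stop rate the effect is small.

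A reader might also infer from item 6 that there is no baseline against which to judge emergent symptoms. The table does mark a baseline SAFTEE, and the PHQ-9 item omits its own tabulated baseline in the same way. This is a wording mismatch only.

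Finally, QIDS, GAD-7 and POMS share the 3-day cadence, so the interval is a general choice. That is fair; the point concerns the absent exit administration, not the interval.

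**Conclusion.** The point holds as a gap in data collection. As scheduled, a patient who stops for side effects before about session 6 has no post-baseline SAFTEE and only unsolicited records. Any by-arm summary of available SAFTEE data would omit these patients and could understate TES side effects.

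The size cannot be derived from the documents. Under the stated assumptions it runs from under 2 percentage points at 2% early stops to 7-9 points at 10%, and the between-arm effect shrinks to the extent that sham patients also stop early. The conclusion rests on reading Protection Against Risks as allowing treatment to end before session 6, which the statement on minimum treatments contradicts. It does not show that a planned result is biased. It is a worthwhile, inexpensive improvement.

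**What to change.** 1. **Add an exit SAFTEE** at the last attended session for every patient, whatever the reason for ending, and keep the every-3-days schedule. Trigger it with the SBJ d/c form for those who withdraw or are withdrawn, and with the end-of-treatment ISI for those who complete. No repeat is needed when the last session is already a SAFTEE session.
2. **Align item 6 with the table**: baseline, every 3 days, and end of treatment or early exit.
3. **State a by-arm report**: SAFTEE in all randomised patients up to session 6, or to exit if earlier, alongside Adverse Event form data. Give the number of sessions received and the number without a form, since exposure will differ for early leavers. Treat later SAFTEE data as descriptive.
4. **Reconcile** the statement on minimum treatments under Procedures with the stopping provisions under Protection Against Risks, and say whether assessments continue after treatment stops.

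The cost is one 5-10 minute online questionnaire for patients leaving off-schedule and a few lines of protocol text. Some patients who leave abruptly will decline it, so the gap would be reduced rather than closed.
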